Appendix

Table A1	Grading of local solicited adverse events following mAb TB31F Administration
Table A2	Grading of systemic solicited adverse events following mAb TB31F Administration
Table A3	Vital signs
Table A4	Laboratory abnormalities

LIST OF ABBREVIATIONS AND RELEVANT DEFINITIONS

ABR	ABR form, General Assessment and Registration form, is the application form that is required for submission to the accredited Ethics Committee (In Dutch, ABR = Algemene Beoordeling en Registratie)
AB	Antibody
AE	Adverse Event
AR	Adverse Reaction
AUC	Area under the serum concentration-time curve
AUC_{0-t}	AUC up to the last measurable concentration
AUC_{0-T}	AUC to the end of the dosing period
BP	Blood pressure
CA	Competent Authority
CBC	Complete Blood Count
CCMO	Central Committee on Research Involving Human Subjects; in Dutch: Centrale Commissie Mensgebonden Onderzoek
C_{max}	Maximum observed serum concentration
CV	Curriculum Vitae
DLT	Dose Limiting Toxicities
DSMB	Data Safety Monitoring Board
EOI	End Of Infusion
EU	European Union
EudraCT	European drug regulatory affairs Clinical Trials
GCP	Good Clinical Practice
GP	General Practitioner
IB	Investigator's Brochure
IC	Informed Consent
IV	Intravenous(ly)
IMP	Investigational Medicinal Product
IMPD	Investigational Medicinal Product Dossier
MC	Medium Care
METC	Medical research ethics committee (MREC); in Dutch: medisch ethische toetsing commissie (METC)
PBMC	Peripheral Blood Mononuclear Cells
pK	pharmacokinetic (pK)

Racc	accumulation index
RUMC	Radboud University Medical Center
(S)AE	(Serious) Adverse Event
SMFA	Standard Membrane Feeding Assay
SC	Subcutaneous(ly)
SPC	Summary of Product Characteristics (in Dutch: officiële productinfomatie IB1-tekst)
Sponsor	The sponsor is the party that commissions the organisation or performance of the research, for example a pharmaceutical company, academic hospital, scientific organisation or investigator. A party that provides funding for a study but does not commission it is not regarded as the sponsor, but referred to as a subsidising party.
SUSAR	Suspected Unexpected Serious Adverse Reaction
T1/2	Terminal serum half-life
TBV	Transmission Blocking Vaccine
Tmax	Time to reach maximum serum concentration
WMO	Medical Research Involving Human Subjects Act (in Dutch: Wet Medisch-wetenschappelijk Onderzoek met Mensen

SUMMARY

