9.2.3 Serious adverse events (SAEs)

A serious adverse event is any untoward medical occurrence or effect that:

- results in death;
- is life threatening (at the time of the event);
- requires hospitalization or prolongation of existing inpatients' hospitalization;
- results in persistent or significant disability or incapacity;
- is a congenital anomaly or birth defect; or

- any other important medical event that did not result in any of the outcomes listed above due to medical or surgical intervention but could have been based upon appropriate judgment by the investigator.

An elective hospital admission will not be considered as a serious adverse event. The investigator will report all SAEs to the sponsor and the safety monitor without undue delay after obtaining knowledge of the events (within 24 hours). All SAEs will be reported through the web portal *ToetsingOnline* to the accredited METC that approved the protocol, within 7 days for SAEs that result in death or are life threatening followed by a period of maximum of 8 days to complete the initial preliminary report by the investigator/sponsor. All other SAEs will be reported within a period of maximum 15 days after the sponsor has first knowledge of the serious adverse event. Death is an outcome of an event. The event that resulted in the death should be recorded and reported on the SAE CRF.

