9.4.3 Recording of adverse event data collection

Study staff will train subjects on use of memory aid booklets for self-assessment of solicited local and general adverse events through 7 days (day of mAb TB31F administration and subsequent 6 days) post- administration of study mAb TB31F; and for self-assessment of adverse events and concomitant medications until day 28. Study staff will review and discuss with the subject all recorded events to ensure appropriate documentation and scoring prior to transferring of the diary card record to the eCRF.

If known, the trial clinician will record the diagnosis (i.e., disease or syndrome) rather than component signs, symptoms and laboratory values. If the signs and symptoms are considered unrelated to an encountered syndrome or disease they should be recorded as individual AEs. If a primary AE is recorded, events occurring secondary to the primary event should be described in the narrative description of the case (e.g. primary AE = Orthostatic hypotension; secondary event may be fainting, head trauma, etc.). In case of hospitalizations for surgical or diagnostic procedures, the pre-existing condition should be recorded as the SAE, not the procedure itself.

All adverse events/reactions (solicited and unsolicited), noted by the investigators will be accurately documented in the case report form by the investigators. For each event/reaction the following details will be recorded:

1. Description of the event(s)/reactions(s)
2. Date and time of occurrence
3. Duration
4. Intensity
5. Relationship with the intervention
6. Action taken, including treatment
7. Outcome

In addition, symptoms will be ranked as (1) mild, (2) moderate, (3) or severe, depending on their intensity according to the following scale:

Mild (grade 1): awareness of symptoms that are easily tolerated and do not interfere with usual daily activity

Moderate (grade 2): discomfort that interferes with or limits usual daily activity

Severe (grade 3): disabling, with subsequent inability to perform usual daily activity, resulting in absence or required bed rest

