9.5 Safety Monitoring Committee

9.5.1 Local safety monitor

For this study, a local safety monitor will be appointed, who will be involved in the review of severe and serious adverse events and volunteer safety. He/she is independent of the sponsor and the investigator. The local safety monitor is notified of all grade III adverse events probably or definitely related to TB31F administration and persisting at grade 3 for >48 hours.

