9.5.4 Safety holding rules

The study may be placed on safety hold at any time for the following reasons:

- On advice of the safety monitor;
- On advice of the Principal/Clinical investigators;
- On advice of the SMC;
- On advice of the accredited METC;
- If holding rules are met (see below).

Holding rules for within-group progression:

If either of the first two subjects within a group meet a holding rule (see below), administration of TB31F will be held for all remaining subjects in that dosage group (and subsequent groups). The following stopping rules apply to subjects within a group:

- One or more participants experience a SAE that is determined to be at least possibly related to the administration of TB31F
- Two or more subjects experience a grade 3 adverse event (local, clinical systemic or laboratory systemic) possibly, probably or definitely related to TB31F administration and persisting at grade 3 for >48 hours

The study site member first aware of the event meeting the holding rule will notify the Principal Investigator and the Local Safety Monitor. The PI will alert the appropriate parties. The SMC will be notified within 24 hours. An ad hoc SMC review will be performed. The following considerations must be discussed:

- Relationship of the AE or SAE to the study product
- Relationship of the AE or SAE to TB31F dose
- If appropriate, additional screening or laboratory testing is provided to other subjects to identify subjects who may develop similar symptoms
- If any study related SAE is not listed on the current informed consent form (ICF), the PI will revise the ICF and subjects will be asked to provide consent on the new ICF

TB31F administration to subjects within the affected group and to the next higher dosage group may resume only if the local safety monitor, PI, SMC and the sponsor agree it is safe to resume TB31F administration. If the accredited METC has recommended safety hold, re-initiation of the study will require METC concurrence. The accredited METC and PATH REC will be informed of a safety hold by the sponsor. Following discussion, it may be decided to terminate the study.

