Erythema/Swelling	2.5 - 5 cm and does not interfere with activity	5.1 – 10 cm or interferes with activity	> 10 cm or prevents daily activity	Necrosis or exfoliative dermatitis

Table A2 Grading of systemic **solicited** adverse events following mAb TB31F Administration

Systemic AE	Mild (Grade 1)	Moderate (Grade 2)	Severe (Grade 3)	Potentially Life-threatening (Grade 4)
Fever (measured orally)	38.0 – 38.4 (°C) 100.4 – 101.1 (°F)	38.5 – 38.9 (°C) 101.2 – 102.0 (°F)	39.0 – 40 (°C) 102.1 – 104 (°F)	>40 (°C)
Chills	No interference with activity	Some interference with activity	Significant; prevents daily activity	ER visit or hospitalization
Fatigue	No interference with activity	Some interference with activity	Significant; prevents daily activity	ER visit or hospitalization
Headache	No interference with activity	Repeated use of non-narcotic	Significant; any use of narcotic pain reliever or	ER visit or hospitalization
Myalgia	No interference with activity	Repeated use of non-narcotic	Significant; prevents daily activity	ER visit or hospitalization

Vital Signs

Table A3. Vital signs

Vital Signs	Mild (Grade 1)	Moderate (Grade 2)	Severe (Grade 3)	Potentially Life Threatening (Grade 4)
Fever (°C)	38.0 – 38.4	38.5 – 38.9	39.0 – 40	> 40
Tachycardia (beats/minute)	101 – 115	116 – 130	> 130	ER visit or hospitalization for arrhythmia
Bradycardia (beats/minute)	50 – 54	45 – 49	< 45	ER visit or hospitalization for arrhythmia
Hypertension (systolic) (mmHg)	141 – 150	151 – 155	> 155	ER visit or hospitalization for malignant hypertension
Hypertension (diastolic) (mmHg)	91 – 95	96 – 100	> 100	ER visit or hospitalization for malignant hypertension
Hypotension (systolic) (mmHg)	85 – 89	80 – 84	< 80	ER visit or hospitalization for hypotensive shock
Respiratory Rate (breaths/minute)	17 – 20	21 – 25	> 25	Intubation

Laboratory abnormalities

Table A4. Laboratory abnormalities

Adverse Event	Intensity Grade	VALUE TB31F
Hemoglobin , male (mmol/L)	1	7.8-8.3
	2	6.5-7.7
	3	5.2-6.4
Hemoglobin, female (mmol/L)	1	6.8-7.3
	2	5.9-6.7
	3	5.0-5.8
Increase in Leukocytes (WBC) (cells/mm ³)	1	11,000 – 15,000
	2	15,001 - 20,000
	3	20,001 - 25,000
Decrease in Leukocytes (cells/mm ³)	1	2,500 - 3,500
	2	1,500 - 2499
	3	1,000 -1,499
Decrease in Platelets (cells/mm ³)	1	125,000 – 140,000
	2	100,000 - 124,000
	3	25,000 – 99,000
Creatinine, mg/dL	1	1.5-1.7
	2	1.8-2.0
	3	2.1-2.5
Transaminases (AST) (U/L)	1	1.1-2.5 x ULN
	2	2.6-5 x ULN
	3	5.1-10 x ULN
Transaminases (ALT)	1	1.1- 2.5 x ULN

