**Analyses in relation to endpoints**

**Safety outcome analyses:**

- For each solicited (local or general) adverse event type, the number and proportion of subjects experiencing that AE within the Protocol-defined timeframe will be tabulated by severity grade for each dose group and for the entire study population. This will also be tabulated for subjects experiencing any solicited local, any solicited general and any solicited AE (see example table below). Where applicable, we will compare these proportions between groups. Relatedness (possibly, probably or definitely) of solicited AEs to TB31F administration may also be presented. (Outcome measures 1 and 2).
- For each unsolicited adverse event type (categorized by ICD-10), the number of events per dose group and overall study population will be described categorized by severity grade and relation to TB31F administration. (Outcome measure 4).
- The proportion of individuals with grade 1, 2 and 3 adverse events may be compared between groups (Outcome measures 1,2,4) .
- The total number of grade 1, 2 and 3 adverse events as count data may be compared between groups.
- Individual serious adverse events (SAEs) will be summarized, including relatedness to TB31F administration (Outcome 5).
- Withdrawals due to AEs/SAEs will be summarized per group.

Table - Descriptive statistics for subjects experiencing solicited AEs

|               |           | Group 1   |   | Group 2   |   | Group 3   |   | Group 4   |   | Group 5   |   | All       |   |
|---------------|-----------|-----------|---|-----------|---|-----------|---|-----------|---|-----------|---|-----------|---|
|               |           | #Subjects | % | #Subjects | % | #Subjects | % | #Subjects | % | #Subjects | % | #Subjects | % |
| Local AE1     | Grade 1   |           |   |           |   |           |   |           |   |           |   |           |   |
|               | Grade 2   |           |   |           |   |           |   |           |   |           |   |           |   |
|               | Grade 3   |           |   |           |   |           |   |           |   |           |   |           |   |
|               | Any grade |           |   |           |   |           |   |           |   |           |   |           |   |
| Local AE2     | Grade 1   |           |   |           |   |           |   |           |   |           |   |           |   |

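### The second holding criterion and the monitor notification count only grade 3, so a related, non-serious grade 4 event graded by Tables A1–A3 can miss both

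*Protocol*

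**What the plan says.** Protocol 9.5.4 gives two holding criteria within a group. Under the first, one SAE at least possibly related to TB31F is enough, whatever its grade. The second needs two or more subjects with a grade 3 event that is "possibly, probably or definitely related to TB31F administration and persisting at grade 3 for >48 hours". Under 9.5.1 the local monitor for safety is to be "notified of all grade III adverse events probably or definitely related to TB31F administration and persisting at grade 3 for >48 hours". Neither text extends to higher grades.

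Appendix 1 does define a higher grade. Table A2 is titled "Grading of systemic solicited adverse events following mAb TB31F Administration", and Table A1 is its local counterpart. Both have a fourth column headed "Potentially Life-threatening (Grade 4" (closing bracket not shown), and Table A3 for vital signs has one too. Fever is grade 3 from 39.0 to 40 °C and grade 4 above 40 °C. For erythema/swelling, grade 4 is "Necrosis or exfoliative dermatitis".

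Elsewhere grade 3 is the top. In 9.4.3, "symptoms will be ranked as (1) mild, (2) moderate, (3) or severe, depending on their intensity according to the following scale", with severe as the last step. Table A4 (laboratory) ends at grade 3. The SAP's safety analyses say "The proportion of individuals with grade 1, 2 and 3 adverse events may be compared between groups", and its table shell has no grade 4 row. The protocol does not say which scale governs the holding rule.

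**The concern.** Whether a worse event counts towards a hold should not depend on which of two grading scales the site applies. On the 9.4.3 scale an event recorded as severe is grade 3 and counts. On Tables A1–A3 the same event can be grade 4. It then does not count unless it also spends more than 48 hours at grade 3.

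The SAE criterion does not close this gap automatically. The SAE definition in 9.2.3 requires an actual threat to life when the event occurs, whereas the tables speak of a potential one. Fever above 40 °C and local necrosis are not listed there. The remaining route is the clause on important medical events kept from a listed outcome by intervention but which "could have been based upon appropriate judgment by the investigator", and that is a matter of judgement.

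A met holding rule is what makes SMC notification within 24 hours and an ad hoc review mandatory (9.5.4). If none is met, dosing within the group goes on with no outside SMC review (9.5.3). Group 5 is the first subcutaneous use, so injection-site reactions are the relevant local case. It is also the last group, so there is no next group whose start depends on a prior SMC recommendation.

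**Working it through.** The plan gives no figure for the holding rule, so there is none to reproduce. The check applies the text to cases.

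**1. Which rows are affected.** The gap needs a grade 4 that describes a lasting state. Where grade 4 is an ER visit or hospitalization, the symptom itself can still be at grade 3, so no gap is claimed for those rows.

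- Tables A1–A2, 7 rows: 5 (pain, chills, fatigue, headache, myalgia) use ER visit or hospitalization; 2 (fever, erythema/swelling) describe a state. 5 + 2 = 7.
- Table A3, 7 rows: 5 use ER visit or hospitalization, 1 uses intubation, 1 repeats fever. 5 + 1 + 1 = 7.
- Distinct terms affected: 2.

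**2. Fever examples.** Inputs: the Table A2 cut-offs; one temperature reading per day (8.3.10); two subjects with related, non-serious fever; four readings 24 h apart. Assumption: duration runs from the first to the last consecutive reading at the required grade, and must exceed 48 h. Four readings span 3 × 24 = 72 h; two span 24 h. A change in intensity gets a new AE description (9.4.3), which supports ending the grade 3 spell in case C when the fever passes 40 °C. The 9.4.3 column assumes the event is recorded as severe.

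| Case | Readings | Table A2, current text | 9.4.3 scale, current text | Grade 3 or higher, time added (either scale) |
|---|---|---|---|---|
| A | 39.5 °C × 4 | 72 h, 2 of 2 count | 72 h, 2 of 2 | 72 h, 2 of 2 |
| B | 40.5 °C × 4 | 0 h, 0 of 2 count | 72 h, 2 of 2 | 72 h, 2 of 2 |
| C | 39.5 °C × 2, then 40.5 °C × 2 | 24 h, 0 of 2 count | 72 h, 2 of 2 | 72 h, 2 of 2 |

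**3. Mixed pairs.** Take two subjects with related, non-serious events lasting more than 48 h, each at one grade throughout. Under Tables A1–A3 the pair (3, 3) meets the current criterion; (3, 4) and (4, 4) do not. With *grade 3 or higher*, all three do.

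**4. Effect on dosing in group 5.** At the minimum intervals in Table 2, subject 1 is dosed at 0 h, subject 2 at 48 h, subject 3 at 96 h, and subjects 4 and 5 at about 97 and 98 h. The criterion needs two subjects. An event in subject 2 can exceed 48 h only after 48 + 48 = 96 h, when subject 3 is due and subjects 4 and 5 follow within about two hours. At minimum spacing the correction therefore stops no dose in practice. Table 2 allows longer intervals, and then at most three people (subjects 3–5) are affected.

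**The case against.** The strongest reply is that the gap is mostly one of labelling. Section 9.4.3 covers the recording of all AEs, and the SAP and Table A4 match its three grades, so on that scale nothing is missed. The scenario also needs several unlikely conditions together: two subjects with lasting related events, at least one of them grade 4, and none judged serious. An investigator could well call such a fever or an injection-site necrosis an important medical event. One related SAE then triggers a hold, which is stricter than the wording proposed here. Investigators, monitor, SMC and ethics committee can each prompt a hold at any time, the monitor takes part in reviewing severe and serious events, and groups 1–4 had no grade 3 AEs or SAEs (13.2). The way of measuring persistence is an assumption, and a safety team may read persisting at grade 3 as not having improved below it. The SMC charter, which also holds the rules (9.5.3), was not available and may already settle the wording.

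All of this limits the reach and none of it closes the gap. Tables A1–A2 are titled as the grading of solicited events, so a site that uses them is following the protocol. Judgement and discretionary holds are not the mandatory trigger.

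It can also be said that a necrotic lesion may exceed 10 cm and so meet grade 3, just as a symptom can after an ER visit. The cases differ: an ER visit is a momentary event, while necrosis is a continuing state that Table A1 places in grade 4.

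**Conclusion.** The concern holds, as a minor point. Read literally, the second holding criterion and the monitor notification leave out a related, non-serious grade 4 event graded by Tables A1–A3 unless it also spends more than 48 h at grade 3. The documents disagree on whether grade 4 is used at all. What can be lost is mainly the mandatory SMC notification and ad hoc review, plus a hold for up to three people if group 5 is dosed more slowly than the minimum. The conclusion rests on three conditions: the site grades by Tables A1–A3, the event is not judged an SAE, and persistence is measured at the stated grade.

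**What to change.** In 9.5.4, second criterion, change *grade 3* to *grade 3 or higher* in both places where it occurs, and add: *Time at grades 3 and 4 within one episode is added together.* In 9.5.1, change *grade III* and the later *grade 3* to *grade 3 or higher*. This wording works whether or not grade 4 is used, and it leaves the two-subject and 48-hour requirements as they are. Align the SMC charter if its text matches.

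The cost is a wording change in two protocol sections and possibly the charter, with no extra data. The downside is that a hold or an ad hoc SMC review may occur slightly more often.

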10. STATISTICAL ANALYSIS

All data will be collected and verified prior to analysis. All data will be analyzed in accordance with the Statistical Analysis Plan. Final analyses of all data will occur after study completion and final verification of data according to GCP. All data analyses will be conducted using IBM SPSS and R using the latest version available. Detailed statistical procedures, listings, table shells, and figures will be provided in a SAP prior to analysis. The SAP will be finalized before study close-out and database lock. The following key statistical components will be considered and a detailed description will be documented in the SAP:

- Primary and secondary endpoints and how they will be measured
- Statistical methods and tests that will be used to analyze the endpoints
- Strategy that will be used if the statistical test assumptions are not satisfied
- Indication of whether the comparisons will be using one-tailed or two-tailed *t*-test (with justification of the choice) and the level of significance to be used
- Identification of whether any adjustments to the significance level or the overall P-value will be made to account for any planned or unplanned subgroup analyses or multiple testing

- Specification of potential adjusted analyses and a statement with which covariates or factors will be included
- Planned exploratory analyses and justification of their importance
- Any subgroup effects with biological justification and support from within and outside the study

10.1 Primary study parameter(s)

The number of subjects enrolled, completed, or withdrawn will be summarized. Reasons for withdrawal, when known, will be provided. Demographic data will be summarized by descriptive statistics and will include total number of observations (n), mean, standard deviation (SD) and range for continuous variables, and number and percentages for dichotomous variables. The primary safety, and reactogenicity outcomes will include all subjects who meet the eligibility criteria, receive study product mAb TB31F, and for whom safety data are available.

Safety Analyses

For the safety analysis, data from all subjects who received a dose of mAb TB31F and for whom safety data are available will be included. All analyses will be descriptive. Data will be presented by dose, overall/dose and overall/subject. Results will be summarized by study group. The percentage of subjects with at least one local AE (solicited and unsolicited), with at least one general AE (solicited and unsolicited) and with any AE during the solicited follow-up period will be tabulated with exact 95% CI (two-sided). No multiplicity adjustment will be implemented in analysis. The same calculations will be performed for AEs rated as grade 3. The percentage of subjects reporting each individual solicited local and general AE during the solicited follow-up period will be tabulated with exact 95% CI. The same tabulation will be performed for grade 3 AEs and for AEs with relationship to mAb TB31F administration. The reports of unsolicited AEs will be reviewed by a physician and will be categorized by ICD-10. The percentage of subjects with at least one report of unsolicited AE and reported up to 28 days after mAb TB31F administration will be tabulated with exact 95% CI. The same tabulation will be performed for grade 3 unsolicited AEs and for unsolicited AEs with a relationship to mAb TB31F administration. SAEs will be described in detail. Withdrawals due to AEs/SAEs will also be summarized. Vital signs which are outside of the normal range and clinically significant will also be listed in tables. The frequency of signs and symptoms will be compared between groups with the chi-square test or fishers exact test. Serious adverse events (SAEs) occurring at any point during the trial will be summarized and relatedness to vaccine will be assessed.

Clinical Laboratory Data Analyses

Any clinically important deviations in routine laboratory test results and/or vital signs as determined by the investigator will be listed. Isolated laboratory abnormalities will be reported as AEs if they are considered clinically relevant by the investigator. Vital signs which are considered clinically

relevant by the investigator will be summarized. All adverse events will be listed by participant and will include details of onset time, duration, severity and relationship to the study product.

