2.2 Study Objectives

Primary objective:

- To assess the reactogenicity and safety after a single dose of mAb TB31F in terms of rates of solicited local AEs through 7 days post-administration, solicited general AEs through 28 days post- mAb administration, clinically significant hematological and biochemical laboratory abnormalities through 28 days post-mAb administration, unsolicited AEs through end of study (day 84), and serious adverse events (SAEs) through end of study.

Secondary objectives:

- To describe the serum pharmacokinetics (pK) of mAb TB31F at each dose level in healthy subjects.
- To assess the pharmacodynamics of mAb TB31F assessed as functional activity of serum in a standard membrane feeding assay at each dose level.

Exploratory objectives:

- To describe the anti-TB31F antibody response (anti-idiotypic) in terms of seropositivity rates and geometric mean titers (GMTs).
- To develop an integrated population pharmacokinetic-pharmacodynamic model for TB31F.

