2.3 Study Endpoints

Primary outcome endpoints:

- Number and severity of solicited local adverse events of all severities from first product administration through day 7;
- Number and severity of solicited general AEs and clinically significant hematological and biochemical laboratory abnormalities from first product administration through day 28;
- Number and severity of unsolicited adverse events from first product administration through end of study;
- Occurrence of serious adverse events from first product administration through end of study.

Secondary outcome endpoints

- Serum pharmacokinetics at each dose level through end of study by ELISA;
- Percentage of transmission reducing activity at different time points by SMFA.

Exploratory outcome endpoints

- Anti-drug antibody (ADA) levels in study subjects after receiving study product through end of study;
- An integrated population pharmacokinetic-pharmacodynamic model by Monte Carlo simulations.

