8. METHODS

8.1 Study parameters/endpoints

8.1.1 Primary study parameters/endpoints

- Occurrence of solicited local adverse events of all severities from first product

administration through day 7;

- Occurrence of solicited general AEs and clinically significant hematological and biochemical laboratory abnormalities from first product administration through day 28;
- Occurrence of unsolicited adverse events from first product administration through end of study;
- Occurrence of serious adverse events from first product administration through end of study.

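### The only dedicated percentage of subjects with an unsolicited AE stops at day 28, although the primary objective and endpoint run to day 84

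*Protocol*

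**What the plan says.** **Objective and endpoint.** The primary objective (Protocol 2.2) is a list of safety outcomes introduced as rates: "in terms of rates of solicited local AEs through 7 days post-administration". Later in the same list it names "unsolicited AEs through end of study (day 84". The endpoint in Protocol 2.3 is "Number and severity of unsolicited adverse events from first product administration through end of study", and SAP outcome measure 4 uses the same words. Protocol 8.1.1 has "Occurrence of unsolicited adverse events from first product administration through end of study". The schedule in 8.3.18 collects unsolicited AEs over days 0 to 84, and 9.4.2 also sets an 84-day period.

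**Analysis in Protocol 10.1.** Unsolicited AEs have one percentage of their own, the share of subjects "with at least one report of unsolicited AE and reported up to 28 days after mAb TB31F administration will be tabulated" with an exact 95% CI. The next sentence extends it: "The same tabulation will be performed for grade 3 unsolicited AEs and for unsolicited AEs with a relationship to mAb TB31F administration". An earlier sentence in 10.1 covers subjects with at least one local AE and at least one general AE, solicited and unsolicited together, and ends "with any AE during the solicited follow-up period will be tabulated with exact 95% CI (two-sided". The section closes with a listing: "All adverse events will be listed by participant and will include details of onset time, duration, severity and relationship to the study product".

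**SAP.** Confidence intervals are referred back to protocol section 10. For solicited AEs, the SAP requires the number and proportion of subjects by grade. For unsolicited AEs, it requires the number of events by severity and relatedness, without a day limit. A comparison of the proportion of individuals with AEs of grades 1 to 3 is optional and cites outcome measure 4. The only AE table shell is for solicited AEs and writes out grades 1 to 3 and any grade.

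**The concern.** The rate that 10.1 asks for does not cover the period that 2.2 and 2.3 define. A report that follows the text exactly would show, for unsolicited AEs, a subject percentage with CI to day 28 and event counts to day 84. It would not show a subject percentage with CI to day 84. A reader wanting the rate named in the primary objective would have to rebuild it from the listing.

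Event counts cannot stand in for that rate, because one subject may contribute several events. In a first-in-human trial with groups of 5, the number of people affected is the figure a reader looks for first.

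A smaller point concerns severity. Appendix 1, Tables A1 to A3, defines grade 4, but the severe repeats in 10.1 name grade 3 only.

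**Working it through.** **1. The documents' own safety figure.** Protocol 4.4 states, for n = 20, a 90% chance of at least one event at a true rate of 10.87% and a 90% chance of none at 0.52%.

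- 1 − (1 − 0.1087)^20 = 0.8999
- (1 − 0.0052)^20 = 0.9010

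Both reproduce. They do not depend on the window, and sample size is not at issue.

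**2. Time outside the dedicated percentage.**

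- (84 − 28) / 84 = 56/84 = 66.7%.
- Scheduled visits after day 0 in groups 1–4 are days 1, 2, 7, 14, 21, 28, 56 and 84, so 2 of 8 fall after day 28. Group 5 adds days 4 and 10, giving 2 of 10.
- Post-dose safety draws in 8.3.11 are days 1, 2, 7, 14, 21, 28 and 84, so 1 of 7 falls after day 28.

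**3. What one subject changes.** Exact (Clopper-Pearson) 95% limits for x of n are the 0.025 quantile of Beta(x, n − x + 1) and the 0.975 quantile of Beta(x + 1, n − x). The lower limit is 0 when x = 0, and the upper limit is 100% when x = n.

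| x/n | % | exact 95% CI |
|---|---|---|
| 1/5 | 20 | 0.5–71.6 |
| 2/5 | 40 | 5.3–85.3 |
| 5/5 | 100 | 47.8–100 |
| 0/25 | 0 | 0–13.7 |
| 1/25 | 4 | 0.1–20.4 |
| 2/25 | 8 | 1.0–26.0 |

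Take one further subject whose first unsolicited AE comes after day 28. A group moves from 1/5 to 2/5 (20 points) and the total from 1/25 to 2/25 (4 points).

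**4. Why counts do not substitute.** Five events in a group of 5 may come from one subject (20%, 0.5–71.6%) or from five (100%, 47.8–100%).

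**5. Illustration of the gap (assumption).** The documents give no rate of unsolicited AEs. If the rate of first events were constant, a share p by day 84 would appear at day 28 as 1 − (1 − p)^(28/84):

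| p by day 84 | shown at day 28 | expected subjects of 25, day 28 vs day 84 |
|---|---|---|
| 20% | 7.2% | 1.8 vs 5 |
| 40% | 15.7% | 3.9 vs 10 |
| 60% | 26.3% | 6.6 vs 15 |
| 80% | 41.5% | 10.4 vs 20 |

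If first events cluster soon after dosing, the gap is smaller. If every first event falls by day 28, there is none.

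**6. Grade 4.** Fever above 40 °C is grade 4 in Tables A2 and A3 and need not be serious. As 10.1 is worded, one such event in 25 subjects leaves the severe row at 0/25 (0–13.7%) instead of 1/25 (4%, 0.1–20.4%).

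**The case against.** **The endpoint is a number and severity, and the SAP delivers that to end of study.** This stands. A reader might infer that the primary endpoint is not analysed after day 28, or that late AEs are lost. The documents do not support either. The SAP counts have no day limit, the participant listing gives onset time, and SAEs at any point are summarised. The SAP also promises the safety committee an AE summary after 84 days' follow-up in all five groups. What remains is the rate named in the objective.

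**Other text may supply the percentage.** Protocol 10.1 says data will be presented by dose and by subject overall, and the SAP presents binary data as counts and proportions. These are general presentation rules. They name neither an unsolicited-AE percentage to day 84 nor a CI.

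The solicited follow-up limit may also apply only to the any-AE item, which would leave the local and general percentages without a day limit. The text is open on this. Even on that reading, those rows pool solicited with unsolicited AEs. Protocol 13.2 reports solicited fatigue in 12 of the 20 intravenous subjects. Those 12 (60%) would already count in a general-AE row, and a later unsolicited event in them would not change it.

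**Reporting date.** Read literally, a cut on reporting could drop an AE with onset by day 28 that is first mentioned at Visit 9, which may fall on day 30 (28 + 2, Table 3). That depends on a literal reading of ordinary wording, so it is only a reason to specify onset date, not a separate defect.

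**Grade 4.** A reader might infer that grade 4 unsolicited AEs or laboratory values drop out of the severe row. The documents do not support that, because the general scale in 9.4.3 and Table A4 stop at grade 3. Grade 4 events involving hospital admission would generally be SAEs and described individually. The any-grade row of the SAP shell, which is only an example, would still count a grade 4 event. The point is confined to non-serious grade 4 solicited AEs and vital signs.

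**Conclusion.** The mismatch is real and worth correcting, but it is a gap in a required summary and not in the data or the endpoint. Protocol 10.1 limits the only dedicated unsolicited-AE subject percentage with exact CI, and its grade 3 and related subsets, to the first third of the period in the primary objective. The SAP refers CIs back to that section and does not require the missing figure.

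The 67% is follow-up time outside the percentage. It should not be read as a share of events missed, since the documents give no event rate. The one-subject shifts of 20 and 4 points are arithmetic. Whether they occur depends on a subject having a first unsolicited AE after day 28. With 5 per group the intervals overlap heavily in any case, so the issue is correct description and not inference.

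The grade 4 labelling is minor, and its 1/25 example is hypothetical. Protocol 13.2 reports no grade 3 AE or SAE in groups 1–4.

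**What to change.** - In Protocol 10.1 and the SAP, tabulate n, % and exact 95% CI of subjects with any, severe and related unsolicited AEs. Use onset date, run through the end-of-study visit, and show each group and overall. Keep day 28 as an additional cut.
- State whether the solicited follow-up limit applies to the local and general AE percentages or only to the any-AE percentage.
- Minor: label the severe rows as grade 3 or higher, and add a grade 4 row to the SAP shell.
- Reconcile three sets of passages. No rule is proposed for any of them:
  - The day counts in 9.4.2 (days 0–6, 0–27, 0–83) against 2.3 and 8.3.18 (to days 7, 28, 84).
  - The memory-aid period in 8.3.4 (day 84) against 9.4.3 (day 28).
  - The grading in 9.4.3 (1–3), Appendix 1 (1–4 in Tables A1–A3) and the grade 3 wording in 9.5.4.

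For the analysis items, the cost is protocol and SAP wording, one added table and one edited shell. AE data are already collected to day 84, so no new data and no change in sample size are needed.
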